The source and nature of this stimulus remains unclear but likely reflects the presence of microbes within the implant-abutment and the crown interface, as reported in clinical studies (Quirynen and van Steenberghe, 1993; Persson *et al.*, 1996). The presence of microbes may be due from either contamination during implant placement or also at abutment connection. It is possible that microorganisms transit from the oral environment into the implant-abutment interface at prosthetic installation (Persson *et al.*, 1996). The phenomenon of microleakage has been described for most implant systems tested (Quirynen *et al.*, 1994; Jansen *et al.*, 1997; Guindy *et al.*, 1998; Gross *et al.*, 1999). Microbial access through the microgap has been reduced by use of washers between components, cement *vs.* screw-retained restorations, or inter-component varnish application (Besimo *et al.*, 1999; Piattelli *et al.*, 2001; Rimondini *et al.*, 2001). Additional evidence that the persistent inflammatory stimulus originates at the microgap interface is supported by data generated that show that when the interface is removed, only small amount of peri-implant inflammatory cells are found (Broggini *et al.*, 2003).

The amount of crestal bone lost after placement of a transmucosal abutment is usually less than 2 mm and unless there is chronic mucosal inflammation it is self-limiting. Nevertheless, crestal bone regression has clinical relevance because esthetic and restorative demands encourage the placement of implants in a more apical position. Relative to the original alveolar crest, crestal and subcrestal implants have demonstrated greater bone loss than have implants placed supracrestally (Todescan *et al.*, 2002; Piattelli *et al.*, 2003). Additionally, differences in response may exist for implants (Abrahamsson *et al.*, 1997) whose abutments have not been manipulated during healing (Todescan *et al.*, 2002).

Biomet3i with over 20 years of dental implant design and commercialization has developed a new implant surface. The new T3 implant will combine a roughened surface in conjunction with the design features of the current Certain™ Tapered Implant System. This study will evaluate the T3 system for the preservation of alveolar crestal bone that is lost after the placement of a

- Quirynen M, van Steenberghe D Bacterial colonization of the internal part of two-stage implants: An in vivo study. *Clin Oral Impl Res* 1994 5: 239
- Todescan *et al.*, 2002
- van Steenberghe D , Naert I, Jacobs R, Quirynen M. Influence of inflammatory reactions vs. oclusal loading on periimplant marginal bone level. *Advan Dental Res* 1999 13:130-135

OBJECTIVES

General Objective

This prospective, multicenter, randomized-controlled clinical study will evaluate the safety and performance of the T3 implants with a modified implant surface and make comparisons against the legacy Nanotite Certain Tapered Implant System for the amount of alveolar crestal bone loss after the placement of a transmucosal abutment.

Specific objectives include:

1. To document the integration success of all study implants by measuring and documenting implant immobility and resonance frequency assessment for up to 5 years.
2. To assess duration of failure-free performance while supporting restorations for five years
3. To measure and document the radiological changes in peri-implant crestal bone levels.
4. To measure and document insertional torque forces using torque-indicating ratchet wrenches.
5. The enrollment of at least 100 patients (up to 200 implants) within three months.

STUDY DESIGN

This will be a prospective, randomized-controlled study in which qualified patients with partial edentulism will be treated with at least two dental implants. Implant sites will be randomly assigned to receive either a test (T3 Nanotite Certain Tapered Prevail - BNPT) or control (Nanotite Certain Tapered - NINTxx) implant (80:20 – test – control randomization ratio). All implants will be placed in a single-stage manner using torque-indicating instruments to document the torque-insertion profile. At implant placement surgery test implants will receive Encode healing abutments whereas control implants will be provisioned with prefabricated or standard abutments. For the test group an Encode Level Impression will take place at 10 weeks and individual final abutments and prosthesis placement at 3 months following implant placement surgery. A fixture level impression will be taken for control implants at week 10, followed by final restorations at month 3. All implants will be allowed to integrate without occluding forces and all restorations will be cemented. Resonance frequency assessment procedures will be done at implant placement surgery and at prosthesis insertion. Cumulative success rate and crestal bone regression will be the primary study endpoint. Enrollment will continue until 100 patients have completed final prosthetic treatment at the participating study centers. Additional control cases will be derived from on-going clinical trials of the NINT implants matched with the prospective study control group for baseline variables, restorative type (STR, fixed bridges), and implant dimensions. The additional control cases will bring the test and control groups to a 1:1 ratio and allow for more powerful analyses.

Study (null) hypothesis:

The functional success (survival and success rate) of the T3 implant to maintain integration and support of prostheses in this study will be no different than of the control implant. Moreover there crestal bone changes that take place after placement and loading of the T3 Certain Tapered Prevail (BNPTxxx – test implant) and Certain Tapered (NINTxx - control implant) will be the same.

[figure not shown]
MATERIALS AND METHODS

Implants with similar geometry but with different surface roughness will be evaluated. All implants are titanium root-form dental implants. The test implant has an integrated platform switch feature, whereas the restorative components of the control implant will be matched.

The **test implant** surface is fashioned using calcium phosphate grit blasting and then etched using the Osseotite® dual acid-etching (DAE) process that establishes a surface roughness (Sa of about 1.2). The blasted and etched surface is present from the implant apex to 1.5 m from the implant collar above this is the original Osseotite surface (Sa 0.6) to the abutment seating surface. The entire length of the test implant has a discrete crystalline deposition of Calcium Phosphate nanoparticles (DCD). Implant length and diameter will be up to the discretion of the investigator within the limits of the following configurations.

4.0mm (D) x 3.4mm (P)	5.0mm (D) x 4.1mm (P)
BNPT4385	BNPT5485
BNPT4310	BNPT5410
BNPT4311	BNPT5411
BNPT4313	BNPT5413

Like the test implants the **control implants** consist of the same internal connection. The NanoTite Tapered implant (Biomet3i) is a threaded titanium alloy (Ti6Al4V) root-form dental implant featuring an internal connection system and associated restorative components. The Osseotite acid-etched surface is present from the apex to the bottom of the machined collar. To the acid-etched surface is added the NanoTite surface treatment of discrete crystalline depositions of calcium phosphate. These crystals range in length from 20 to about 100 nanometers. Restorations will be constructed using Biomet 3i components.

All implants will be available in diameters of 4 and 5 mm and lengths of 8.5, 10, 11.5, and 13 mm.

Patient Sample

A total of 100 patients will be enrolled in the study. Each qualified study patient will provide at least two implants to the data set. Enrollment will continue for three months or until 100 qualified patients (contributing at least 200 implants) have completed final prosthetic treatment. A qualified patient is one who meets admission criteria and has provided informed consent. Each patient will receive **either** test or control implants. Each patient will be randomly assigned to receive either Test or Control implants.

Patient Numbering

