A global evaluation of the status of the area where the study implants were placed will be recorded using gingival and plaque indices. The **gingival index** will be ranked as follows: (0) Normal gingiva; (1) Mild inflammation, slight change in color, slight edema, no bleeding on probing; (2) Moderate inflammation, redness, edema and glazing, bleeding on probing; (3) Severe inflammation, marked redness and edema, ulcerations; tendency toward spontaneous bleeding.

The criteria for **plaque index** are as follows: (1) No plaque in gingival area; (2) No plaque visible by the unaided eye, but plaque is made visible on the point of the probe after it has been removed across surface at entrance of gingival crevice; (3) Marginal area is covered with a thin to moderately thick layer of plaque; deposit is visible to the naked eye; (4) Heavy accumulation of soft matter, the thickness of which fills out a niche produced by gingival margin and tooth surface; interdental area is stuffed with soft debris.

EVALUATION CRITERIA

Implant Integration Success

An implant will be considered successful if it is immobile at specific points in time. Additionally, long-term implant success will be achieved when tested with instrument pressure at follow-up evaluations with no evidence of persistent peri-implant radiolucency, no persistent or irreversible signs and symptoms of pain, infection, neuropathies, or paresthesia.

Additionally the correlation of initial stability (as reflected in the Insertion Torque Profile) and clinical success will be assessed. The individual implant will be considered the experimental unit. The Insertion Torque Profiles for failed implants will be compared with those from successful implant cases to determine if this baseline variable is predictive.

Radiological Crestal Bone Level Changes

Bone levels measured at three and six month, and all follow-up intervals from both treatment groups will be compared to those measurements observed at the time of implant placement surgery to derive *changes from baseline* values. Differences between groups will be calculated and used to determine if the crestal bone changes are different between groups. A difference of 5% will be considered relevant.

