- Probably related - an event that follows a known or suspected response pattern, is confirmed by improvement upon stopping or reducing treatment, and cannot be reasonably explained by the known characteristics of the patient's clinical state.
- Definitely related - an event that follows a known or suspected response pattern, is confirmed by improvement upon stopping or reducing treatment, and reappears upon repeated exposure.
- Unknown - relationships for which insufficient information exists.

Failure to use an implant due to improper placement is not an adverse event in the absence of pathology, but is censored data for the survival analysis and must be reported on the Implant Failure Form (ICF).

Medical Adverse Events

Death, serious illness or major trauma, whether implant success is affected or not, is an adverse event and must be reported on the Medical Event form (AME). A medical adverse event will be assessed based on causality (criteria described in dental adverse event section) and severity. Severity criteria are described as follows:

- Mild - the adverse reaction does not interfere in a significant manner with the patient's normal functioning level.
- Moderate - the adverse reaction produces some impairment of functioning but is not hazardous to health; may be uncomfortable.

- Severe - the adverse reaction produces significant impairment of functioning or incapacitation and is a definite hazard to the patient's health; this can lead to 1) death or decreased life expectancy, 2) an immediate life-threatening event, 3) inability to resume usual life pattern, 4) significant disability or incapacity.

STATISTICAL ANALYSES

The primary efficacy parameter will be the duration of implant survival (failure-free utilization or lack of mobility) from implant placement. The fraction of surviving implants and cases at the completion of 1, 2 and 5 years of function will be evaluated. Implant survival differences of >5 % will be considered clinically relevant. Clinical outcomes will be evaluated by clinical signs and symptoms of implant failure and dental and medical events.

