Secondary efficacy parameters will be prosthesis survival and procedural success. For each patient, survival time after study surgery will be calculated by the duration of failure-free, intervention-free, duration of support of a prosthesis. Implant survival curves will be estimated for the Test and Control treatment group and these will be compared using the Log Rank or Wilcoxon tests. Survival rates at six months (Study Visit 6), one-year (Study Visit 7) and 5 years (visit 11) will be computed for each treatment group, and compared using chi-square. The sample size determinations were based upon survival to the five-year point as a measure of efficacy.

A secondary outcome question of this study is the equivalence in the changes in alveolar crestal bone between the modified implant (T3) and its predecessor the Certain™ implant. In previous studies of Biomet3i implants (Calvo-Guirado 2011, Zetterqvist 2009; Östman et al. 2010), crestal bone change-from-baseline values have ranged from a mean of 0.37 mm to 1.2 mm at the six month (Visit 6) time point. For purposes of this study there will be an assumption that the control implant will have a change-from-baseline mean value of 0.75 mm at the 6 month (Visit 6) time period. To declare equivalence the Test implant system will need to have a crestal bone change-from-baseline mean bone level regression of 0.75 ± 0.15 mm; or to declare superiority a mean value of 0.55 mm or lower. For the functional evaluation of crestal bone regression will be determined for each of the treatment groups at 3 months (Visit 5), six months (Visit 6) and at each of the annual study visits. The significance of these changes from baseline will be evaluated at each time point using a paired t-test or a Wilcoxon signed rank test. At each time point the treatment groups will be compared using the analysis of variance or the blocked Wilcoxon test, as appropriate. Analysis to determine association with other variables will use “exact” rather than “asymptomatic” methods where necessary.

The Test and the Control implants will be considered the experimental units. The influence of the length and diameter of the implants as a covariate on survival will be determined during the analysis. The comparability of the Test and Control treatment groups will be determined with regard to demographic

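### The design and statistics sections name different primary endpoints, and the sample size attributed to five-year survival has no stated basis and, at most plausible rates, low power for the 5-point difference called relevant

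*Combined protocol and SAP*

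**What the plan says.** Three statements in the current text set the status of the endpoints.

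- STUDY DESIGN: "Cumulative success rate and crestal bone regression will be the primary study endpoint".
- STATISTICAL ANALYSES, opening paragraph: "The primary efficacy parameter will be the duration of implant survival (failure-free utilization or lack of mobility) from implant placement".
- STATISTICAL ANALYSES, crestal bone paragraph: "A secondary outcome question of this study is the equivalence in the changes in alveolar crestal bone".

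On size, Patient Sample says "A total of 100 patients will be enrolled in the study", each contributing at least two implants. Randomization sets an 80:20 test-to-control ratio. STUDY DESIGN adds matched control cases from other ongoing trials to bring the groups to 1:1. STATISTICAL ANALYSES says "The sample size determinations were based upon survival to the five-year point as a measure of efficacy" and "Implant survival differences of >5 % will be considered clinically relevant". Survival rates are to be compared by chi-square and survival curves by log-rank or Wilcoxon tests. The null hypothesis in STUDY DESIGN is that the two implants do not differ in survival, success or crestal bone change.

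**The concern.** The two sections disagree on which outcome decides the trial, and nothing says which section governs. The survival-type outcome also changes between them. STUDY DESIGN uses a cumulative success rate, whereas STATISTICAL ANALYSES uses time to loss of function or mobility. Under Implant Integration Success, long-term success further requires the absence of persistent radiolucency, pain, infection, neuropathy and paresthesia. An immobile implant with persistent radiolucency would therefore count as surviving but not as a long-term success.

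Two things are at stake. Without a ranking, whichever outcome favours the test implant could be reported as the primary result. And because the hypothesis is framed as no difference, a non-significant survival test could be read as confirming it, even where the test had little chance of detecting the difference that the plan itself calls relevant.

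**Working it through.** **1. Endpoint status, side by side**

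| Outcome | STUDY DESIGN | STATISTICAL ANALYSES |
|---|---|---|
| Cumulative success rate | primary | not named as primary |
| Duration of implant survival | not named | primary |
| Crestal bone change | primary | secondary |

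If either of two primary endpoints could win at 0.05, the family-wise error would be 1 − 0.95² = 9.75% for independent tests, and at most 0.05 + 0.05 = 10%.

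**2. The stated sample size.** It cannot be reproduced, because the documents give no survival rate, power, dropout or formula. Difference-test calculations were tried over 5-point pairs from 85/90% to 94/99% and for 95% against almost 100%, at 1:1 and 4:1, one- and two-sided, with and without continuity correction. None gave 100 or 200.

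**3. Inputs for the check**
- From the documents: 100 patients, at least two implants each, 80:20. This gives 80 × 2 = 160 test and 20 × 2 = 40 control implants, or 160:160 after the top-up. The implant is the unit of analysis.
- Assumed: the 5% means percentage points; significance means two-sided p < 0.05 (the printed sign points the other way); implants are independent; there is no dropout; survival is as shown below.

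**4. Power of the planned chi-square test** (exact enumeration, no continuity correction)

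| Test / control survival | 160:40 | 160:160 |
|---|---|---|
| 95 / 90% | 24% | 39% |
| 90 / 95% | 10.5% | 39% |
| 98 / 93% | 40% | 60% |
| 93 / 98% | 7% | 60% |
| 99 / 94% | 57% | 72% |
| 94 / 99% | 4% | 72% |
| 100 / 95% | 87% | 96% |

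At 160:40, power is lowest when the test implant is the worse one. A log-rank approximation (Schoenfeld) at 160:160 gives 42% for 90 against 95% and 68% for 93 against 98%, so the choice of test does not change the picture.

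**5. Size needed for 80% power, 90 against 95%, 1:1**

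n per arm = [1.96·√(2 × 0.925 × 0.075) + 0.842·√(0.90 × 0.10 + 0.95 × 0.05)]² / 0.05² = (0.730 + 0.312)² / 0.0025 ≈ 435, or 870 implants in total. For 94 against 99% the same method gives 211 per arm, or 422.

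**6. Precision**

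With equal survival S in both arms, the 95% CI half-width is 1.96·√[S(1 − S)(1/n₁ + 1/n₂)].
- S = 95%, 160:40: 1.96·√(0.0475 × 0.03125) = 1.96 × 0.0385 = 7.6 points.
- S = 95%, 160:160: 1.96·√(0.0475 × 0.0125) = 1.96 × 0.0244 = 4.8 points.

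| Survival | 160:40 | 160:160 |
|---|---|---|
| 90% | ±10.4 | ±6.6 |
| 95% | ±7.6 | ±4.8 |
| 98% | ±4.9 | ±3.1 |

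With two implants per patient and an assumed within-patient correlation of 0.3, the design effect is 1 + (2 − 1) × 0.3 = 1.3, and each half-width grows by √1.3 = 1.14. For example, 7.6 becomes 8.6, 4.8 becomes 5.4, and 4.9 becomes 5.5. Dropout would widen them further.

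**The case against.** A reader might infer that this trial cannot resolve, or cannot exclude, a 5-point survival difference. The documents do not support that. They state no survival rate, and the answer depends on it: the half-width is already just under 5 points at 160:40 if survival is 98%, and at 160:160 if it is 95%, before clustering and dropout. If survival is 98% in both arms, a non-inferiority test with a 5-point margin at one-sided 0.025 and 80% power would need 124 implants per arm, which 160:160 would meet on the same optimistic terms. For the same reason, no single half-width can be given as the trial's precision. This objection stands against an absolute claim. It does not rescue the planned analysis, because the plan sets no non-inferiority test or margin for survival, and its difference tests stay under 80% power for every pair in the table except 95 against 100%.

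The 1:1 top-up improves precision, but those controls come from other trials and are not randomized. The 160:160 figures treat them as if they were.

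A reader might also take the near-10% family-wise error as a property of the plan. It is conditional: STUDY DESIGN states no rule that either endpoint may win. The crestal bone claim is also worded as a criterion on the mean ("To declare equivalence the Test implant system will need to have a crestal bone change-from-baseline mean bone level regression of 0.75 ± 0.15 mm"), so its error rate is not 5% by construction. Nor do the documents show any intention to choose between endpoints after the fact; they only leave it open.

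The gap between success and survival is narrower than it may look. Success is first defined as immobility at specific times, close to the survival definition; the further criteria attach to long-term success. Finally, survival is not self-evidently the right primary. The general objective compares the implants on crestal bone loss, and the study title names both outcomes.

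**Conclusion.** The endpoint conflict holds as a matter of text and needs no assumptions: crestal bone is primary in one section and secondary in the other, and the survival-type outcome is not the same measure in both. The missing basis for the sample size is equally plain.

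The power finding is conditional. For two independent implants per patient and no dropout, power for a 5-point difference at 160:40 is 7% to 24% for test/control rates of 93/98, 90/95 and 95/90%. It is higher when the test implant is better and survival is high (40% at 98/93, 57% at 99/94). At 160:160 it is 39% to 72% for pairs from 90/95 to 94/99%. The exception is about 95 against 100%, and at 160:40 only with the test implant the better one. More than two implants per patient would raise these figures before clustering, but the objectives speak of up to 200 implants. The supportable conclusion is that power is well under 80% over most plausible rates, so a non-significant survival test would not support the no-difference hypothesis. Confidence is high on the endpoint conflict and moderate on the size of the power shortfall.

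**What to change.** 1. Use one hierarchy in both sections. The smaller edit keeps implant survival, with one definition, as primary, makes crestal bone change at Visit 6 the first key secondary, and amends STUDY DESIGN to match. If the sponsor wants crestal bone as primary or co-primary, in line with the general objective, amend STATISTICAL ANALYSES instead and state the multiplicity rule.
2. Replace the sample-size sentence with the precision delivered under stated assumptions. For example: for independent implants and no dropout, the 95% CI half-width for the survival difference is 10.4, 7.6 and 4.9 points at 90, 95 and 98% survival for 160:40 randomized implants, and 6.6, 4.8 and 3.1 points for 160:160 including non-randomized controls; clustering and dropout widen these. If the sponsor has a calculation on file, state its rates, alpha, power, dropout and clustering allowance.
3. Report the survival difference as an estimate with its confidence interval set against the 5-point difference, and state that a non-significant test is not read as equivalence.

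The cost is wording in two sections and no additional patients. The drawback is a weaker survival claim.
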